7.1 Efficacy Variables

The efficacy analyses will be based on the FAS and will be done by randomized treatment group (20 U [for final analysis pooled over stages 1 and 2 if not stated otherwise below], 50 U, 75 U, 100 U). Statistical tests will be two-sided hypothesis tests for between-treatment differences in general. Continuous variables (values and changes from baseline) will be summarized by number of values analyzed (n), mean, standard deviation, median, quartiles, minimum, and maximum. [REDACTED]

[REDACTED]

[REDACTED]

[REDACTED]

For qualitative variables, absolute and percent frequencies (n, %) and, if applicable, shift tables will be displayed. Confidence limits [REDACTED] will be given, where appropriate.

[figure not shown]
[REDACTED]

[REDACTED]

[figure not shown]
Mean, first quartile (Q1), median, and third quartile (Q3) will be reported to one decimal place more than the data were collected, for the standard deviation two decimal places more will be displayed; for derived data, an adequate number of decimal places will be chosen. Percentages will be calculated using the denominator of all subjects in a specified population and treatment group. The denominator will be specified in a footnote to the tables for clarification if necessary. Percentages will be reported to one decimal place.

Efficacy analysis will be based on the MP solely, ending with the End of MP visit. (As specified in the CSP, the End of MP visit is performed between Day 180 ± 7 and 360 ± 7 , depending on when the individual subject relapsed to baseline according to the investigator's assessment on the FWS at maximum frown.) Generally, only data from visits until regular End of MP will be used for

efficacy analyses, i.e. data from erroneously performed visits after occurrence of relapse⁶ (V10 to V14 and/or from End of MP visit) will be listed only.

⁶ based on investigator's FWS scores at maximum frown

[figure not shown]

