A further sensitivity analysis will be performed to assess the impact of the COVID-19 pandemic on the primary efficacy analysis. To this end, for each subject with missing values due to COVID-19 pandemic (i.e., in case visits not performed due to COVID-19 or performed virtually due to COVID-19 so that live assessments by investigator could not be performed or discontinuation due to COVID-19 before relapse to baseline status), it will be checked whether values are missing from one or more visits directly preceding the visit when relapse to baseline was observed. While intermittently missing values due to COVID-19 (as well as continuous missingness resulting from premature discontinuation due to COVID-19) are generally assumed to be missing at random, this specific pattern of intermittent missingness might lead to bias in assessment of duration of effect. Specifically, the time to relapse to baseline status might be overestimated. Therefore, a sensitivity analysis will be conducted with time to relapse to baseline status from affected cases being censored at the first visit of those subsequent visits with missing values that directly precede the visit when relapse to baseline was observed. By this means, any overestimation of duration of effect resulting of a possibly delayed observation of relapse to baseline will be ruled out. If the first visit of those subsequent visits with missing values that directly precede relapse was performed virtually due to COVID-19 pandemic, the actual visit date will be used for censoring. In case the respective visit was not performed due to COVID-19 pandemic, time to relapse will be censored at the nominal visit date (calculated as injection date + number of days according to visit schedule in the study protocol - 1). The censoring variable CSNR will be set to 3.

The need for further sensitivity analyses was discussed during BDRMs. During the BDRM for the final analysis performed on 7-JAN-2021, it was confirmed that all randomized subjects fulfill the

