requirements to be included in the FAS. Furthermore, details on premature study discontinuations, amount, patterns and reasons for missing data on the FWS at maximum frown as assessed by the investigator and relatedness to COVID-19 pandemic as well as any identified intercurrent events were closely reviewed and discussed. It was concluded that the assumption of random missingness underlying the primary duration of effect analysis appears reasonable and that the above-specified analysis to account for a specific pattern of missingness due to COVID-19 pandemic was deemed adequate and sufficient to assess the impact of the COVID-19 pandemic on the primary efficacy analysis (see also section 7.4.7 below). No intercurrent events with relevant impact on interpretation of analysis results were identified. Thus, no additional sensitivity analyses were considered necessary.

[figure not shown]

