7.1.2 Secondary Efficacy Variables

[figure not shown]
The secondary duration of effect variables (see section 6.1.2) will be analyzed in analogy to the primary efficacy variable. However, for the final analysis, the Cox regression analysis will be limited to pooling the 20 U groups of both stages.

Duration of effects for each definition will be calculated as described in section 7.1.1, timing and censoring variables will be defined in analogy to the primary efficacy variable.

Kaplan Meier and Cox regression analyses will be performed as described above, except for the sensitivity analysis with separate 20 U groups from stage 1 and 2, which will be only done for the primary variable.

For the percentages of subjects fulfilling the criteria as described in the secondary efficacy variables (see section 6.1.2), two-sided 95% Pearson-Clopper confidence intervals will be computed for percentages of subjects showing an effect in each dose group.

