7.4.1 Discontinuations and Missing Data

[figure not shown]
With relevance to efficacy objectives, the treatment will be applied only once and hence cannot be discontinued. Therefore, no premature discontinuation from treatment can occur. Missing values likewise occur at random or because the subject completes the study early due to relapse to baseline. The latter will not impact the primary analysis of duration of effect since this was completely captured. Hence, for any Kaplan-Meier or Cox regression analysis and inferential statistics, intermittent missing data will be ignored and monotone missingness be considered as censored.

Intermittently missing values due to COVID-19 pandemic (resulting from missing visits not performed due to COVID-19 pandemic or visits performed virtually due to COVID-19 pandemic, thus precluding live assessments by the investigator as needed for the primary efficacy variable) as well as monotonously missing values resulting from premature discontinuation due to COVID-19 pandemic are as well considered missing at random. However, a specific pattern of missing values might introduce bias to assessment of the primary variable of duration of effect: If data are missing from visits directly preceding the visit when relapse to baseline status is observed, time to relapse to baseline status might be overestimated. A sensitivity to assess such impact on missing

values due to COVID-19 pandemic on the primary duration of effect variable is described in section 7.1.1.

Handling of missing values due to the COVID-19 pandemic

Due to the COVID-19 pandemic, a considerable amount of missing data is expected for subjects from stage 2. Restrictions related to COVID-19 in both the US and in Germany (temporarily closed sites, stay-at-home orders, quarantines imposed to subjects suspected to be infected) may make it impossible for many subjects to attend all planned on-site visits. Since live assessments by investigators cannot be performed remotely, this will inevitably lead to missing data.

Handling of missing data due to the COVID-19 pandemic in the final statistical analysis will depend on the number and pattern of missing values, which will be thoroughly described in the clinical study report.

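### Day 180 percentages: the visible all-subjects denominator in SAP 7.1 would let stage 2 COVID-19 gaps dilute 100 U most, and it must be reconciled with SAP 7.4.1

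*SAP*

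**What the plan says.** SAP 7.1 bases efficacy analyses on the FAS by randomized dose group, with 20 U pooled over both stages in the final analysis. Its visible rule for percentages is "Percentages will be calculated using the denominator of all subjects in a specified population and treatment group". The next sentence lets a table footnote specify the denominator where clarification is needed.

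Under SAP 5, a subject enters the FAS with a baseline and one post-baseline value of any efficacy variable, so a Day 180 rating is not required. SAP 7.1.1 reports that at the final blind data review "it was confirmed that all randomized subjects fulfill the" "requirements to be included in the FAS".

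SAP 6.1.2 lists four Day 180 percentages, two from investigator ratings and two from subject ratings. For these, SAP 7.1.2 states that "two-sided 95% Pearson-Clopper confidence intervals will be computed for percentages of subjects showing an effect in each dose group". It gives no visible rule for a missing rating.

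On missing data, SAP 7.4.1 says that "a considerable amount of missing data is expected for subjects from stage 2". It puts intermittent COVID-19 gaps and those from discontinuation on the same footing: values lost through "premature discontinuation due to COVID-19 pandemic are as well considered missing at random". Its general rule is that "for any Kaplan-Meier or Cox regression analysis and inferential statistics, intermittent missing data will be ignored and monotone missingness be considered as censored". SAP 7.4.7 says that stage 1 lost no main period visit to COVID-19. The one COVID-19 sensitivity analysis is in SAP 7.1.1: "A further sensitivity analysis will be performed to assess the impact of the COVID-19 pandemic on the primary efficacy analysis".

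**The concern.** Dividing by all FAS subjects has the same arithmetic effect as counting an unrated subject as not having responded. That is a recognised conservative convention, and where loss is similar across groups it does little harm to their comparison. Here loss follows stage, and stage is tied to dose: 100 U exists only in stage 2, 50 U and 75 U only in stage 1, and pooled 20 U is half of each. An administrative loss could therefore look like a weaker Day 180 response at the highest dose of a dose-ranging study.

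This also sits badly with the plan's own assumption. If the gaps are missing at random, treating them as failures in one set of estimates and not in others puts the four dose groups on different footings. SAP 7.4.7 expects several secondary parameters to be affected as well as the primary one, yet the sensitivity analysis covers only the primary variable.

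**Working it through.** **Group sizes (SAP 3.1; Protocol synopsis).** Stage 1: 150 at 1:2:2 gives 30 / 60 / 60. Stage 2: 90 at 1:2 gives 30 / 60. The total is 150 + 90 = 240, which reproduces the planned number. The stage 2 share s of each group is 60/60 = 1 for 100 U, 30/60 = 0.5 for pooled 20 U, and 0 for 50 U and 75 U.

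**Effect of the default.** Let p be the true Day 180 rate and f the share of each stage 2 arm with no Day 180 rating because of COVID-19. Assume f is equal in both arms and unrelated to response. The expected all-FAS percentage is p(1 − f·s):

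- 100 U: p(1 − f)
- pooled 20 U: [30p + 30(1 − f)p]/60 = p(1 − f/2)
- 50 U and 75 U: p, unchanged by this cause

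In percentage points, 100 U falls by 100·f·p100 and pooled 20 U by 100·(f/2)·p20. The drop at 100 U is the larger whenever p100 exceeds half of p20.

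**Illustrative sizes.** The documents give neither f nor p, so every value below is assumed. Drops are in points, 100 U / pooled 20 U, with the same true rate in both groups:

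| f | p = 20% | p = 50% | p = 70% |
|---|---|---|---|
| 5% | 1.0 / 0.5 | 2.5 / 1.25 | 3.5 / 1.75 |
| 10% | 2.0 / 1.0 | 5.0 / 2.5 | 7.0 / 3.5 |
| 20% | 4.0 / 2.0 | 10.0 / 5.0 | 14.0 / 7.0 |

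With unequal assumed rates of 50% at 100 U and 30% at 20 U, and f = 20%, the difference falls from 20 points to 0.50 × 0.80 − 0.30 × 0.90 = 0.40 − 0.27 = 13 points.

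**Both denominators side by side** (p = 50% in every group, f = 20%, exact 95% Clopper-Pearson intervals):

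| Group | All FAS | Rated only |
|---|---|---|
| 100 U | 24/60 = 40.0% (27.6 to 53.5) | 24/48 = 50.0% (35.2 to 64.8) |
| Pooled 20 U | 27/60 = 45.0% (32.1 to 58.4) | 27/54 = 50.0% (36.1 to 63.9) |
| 75 U | 30/60 = 50.0% (36.8 to 63.2) | unchanged |

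**How much of stage 2 was exposed at Day 180.** SAP 7.4.7 gives the last randomization as 10-OCT-2019 and the pandemic declaration as 11-MAR-2020. SAP 7.1.1 computes a nominal visit date as injection date + day number − 1.

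- Last nominal Day 180: 10-OCT-2019 + 179 days = 06-APR-2020. The window closes 7 days later, on 13-APR-2020.
- Injection date with nominal Day 180 on 11-MAR-2020: 11-MAR-2020 − 179 days = 14-SEP-2019. Only subjects injected from then on had nominal Day 180 on or after the declaration.
- The dose escalation meeting was on 24-JUL-2019 (SAP 7.4.2). Assume even accrual from 27-JUL-2019, three days later, to 10-OCT-2019, a span of 76 days. The exposed share is then 27/76 = 36%, or 34/76 = 45% if the +7-day window is counted.
- On that assumption, f = 20% would need about 45% to 56% of exposed subjects to miss the rating (0.20/0.447 to 0.20/0.355), and f = 5% about 11% to 14%.

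**Subject ratings.** Protocol amendment 2, which deals with home self-assessment during the pandemic, is dated 30-APR-2020. That is 17 days after the last Day 180 window closed. On these dates it would not have protected the two subject-rated Day 180 percentages.

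**The case against.** The strongest objection is that the rule may already exist where the reader cannot see it. SAP 7.1 has blacked-out blocks near the denominator sentence. SAP 9 says that decisions from the final blind data review were added to 7.1. The abbreviation list defines a count of missing observations that the visible text never uses. The denominator sentence also sits in a paragraph on reporting format, and a footnote may name another denominator. All of this stands, and it makes the point conditional.

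Second, a Clopper-Pearson interval is ordinarily an inferential statistic. On that reading the 7.4.1 instruction to ignore intermittent gaps already leads to rated subjects only. This is a fair reading, but it contradicts the default in 7.1, and nothing visible says which prevails.

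Third, little hangs on it. The percentages are secondary and per-group, with no visible between-group test. 100 U and 75 U were not randomized concurrently. The number, pattern and reasons for missing data are to be described in any case. This supports a minor grade, but it does not settle which denominator applies.

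A reader might go further in three ways that the documents do not support:

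- That the SAP imputes non-response. It never says so; this is only the arithmetic result of the visible default.
- That Day 180 loss is considerable. The SAP's expectation concerns stage 2 visits in general, and only late-enrolled subjects reached Day 180 after the declaration.
- That the 100 U result is wrong by a known amount. No rate of loss or response is given.

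**Conclusion.** The point holds as a minor ambiguity with a known direction and an unknown size. If the visible default is followed, COVID-19 loss lowers the Day 180 percentages by a relative f at 100 U, about f/2 at pooled 20 U, and nothing at 50 U and 75 U. This assumes equal loss in both stage 2 arms and planned group sizes. The zero for 50 U and 75 U refers to COVID-19 loss only; ratings missing for other reasons lower any group under the same rule. If 7.4.1 governs the intervals instead, intermittently unrated subjects drop out and this dilution largely disappears. SAP 7.1 and 7.4.1 therefore need one explicit, reconciled rule. If blacked-out text already provides it, nothing more is needed.

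**What to change.** Before stage 2 is unblinded, add to SAP 7.1.2:

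- The main denominator for the four Day 180 percentages, with 7.1 and 7.4.1 worded to agree with it.
- Each percentage and its Clopper-Pearson interval on both bases: all FAS subjects, and FAS subjects with a Day 180 rating.
- A definition of a Day 180 rating as V9, or End of MP performed at Day 180 ± 7, in line with the interim analysis in SAP 7.4.2. Without End of MP, subjects who relapsed by Day 180 could drop out of the rated-only figure and inflate it. State also whether an unplanned on-site rating outside the window counts.
- The number unrated at Day 180 by dose group and stage, in the same table.

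The cost is a few sentences and one extra table, with no new data collection. The rated-only intervals are wider: in the 100 U illustration, 29.6 points (35.2 to 64.8) against 25.9 (27.6 to 53.5). The rated-only figure also relies on missingness being unrelated to response within dose group, which is why both should be shown.

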7.1.1 Primary Efficacy Variable(s)

The primary variable is the duration of effect defined in section 6.1.1, with effect being defined as improvement at maximum frown as assessed by the investigator on the FWS. Duration of effect will be described by Kaplan-Meier Curves per group and the respective medians of times with associated 2-sided 95% confidence interval.

[REDACTED] pairwise log-rank tests will be applied to compare differences between high dose groups (50 U, 75 U and 100 U) and the 20 U group to explore statistical significance. The 20 U group data will be pooled from stage 1 and 2 for the final analysis.

For the primary endpoint, a Cox proportional hazards regression model will be applied to the data with covariates dose group (20, 50, 75, 100 U), study site⁸, and baseline FWS score at maximum frown as assessed by the investigator.

[figure not shown]
The timing and censoring variables for the Kaplan-Meier analysis and the Cox regression model will be calculated [REDACTED]

⁸ The term “center” as used in the description of this model in the CSP was replaced by the “study site” to increase consistency with other parts of the CSP and throughout this SAP. The meaning remains the same.

For the Cox regression analysis in the final analysis, the pooled 20 U group will be used as reference group. Hazard ratios will be calculated for each dose group to the reference group including Wald 95% confidence intervals and two-sided p-values.

For the Cox regression analysis in the interim analysis, the 20 U group will be used as reference group. Hazard ratios will be calculated for each dose group to the reference group including Wald 95% confidence intervals and two-sided p-values.

To explore potential stage effects in the final analysis, a sensitivity analysis will use dose groups 20 (stage 1), 20 (stage 2), 50, 75 and 100 U with 20 (stage 1) as reference group. Depending on the outcome further exploration might be needed.

A further sensitivity analysis will be performed to assess the impact of the COVID-19 pandemic on the primary efficacy analysis. To this end, for each subject with missing values due to COVID-19 pandemic (i.e., in case visits not performed due to COVID-19 or performed virtually due to COVID-19 so that live assessments by investigator could not be performed or discontinuation due to COVID-19 before relapse to baseline status), it will be checked whether values are missing from one or more visits directly preceding the visit when relapse to baseline was observed. While intermittently missing values due to COVID-19 (as well as continuous missingness resulting from premature discontinuation due to COVID-19) are generally assumed to be missing at random, this specific pattern of intermittent missingness might lead to bias in assessment of duration of effect. Specifically, the time to relapse to baseline status might be overestimated. Therefore, a sensitivity analysis will be conducted with time to relapse to baseline status from affected cases being censored at the first visit of those subsequent visits with missing values that directly precede the visit when relapse to baseline was observed. By this means, any overestimation of duration of effect resulting of a possibly delayed observation of relapse to baseline will be ruled out. If the first visit of those subsequent visits with missing values that directly precede relapse was performed virtually due to COVID-19 pandemic, the actual visit date will be used for censoring. In case the respective visit was not performed due to COVID-19 pandemic, time to relapse will be censored at the nominal visit date (calculated as injection date + number of days according to visit schedule in the study protocol - 1). The censoring variable CSNR will be set to 3.

The need for further sensitivity analyses was discussed during BDRMs. During the BDRM for the final analysis performed on 7-JAN-2021, it was confirmed that all randomized subjects fulfill the

requirements to be included in the FAS. Furthermore, details on premature study discontinuations, amount, patterns and reasons for missing data on the FWS at maximum frown as assessed by the investigator and relatedness to COVID-19 pandemic as well as any identified intercurrent events were closely reviewed and discussed. It was concluded that the assumption of random missingness underlying the primary duration of effect analysis appears reasonable and that the above-specified analysis to account for a specific pattern of missingness due to COVID-19 pandemic was deemed adequate and sufficient to assess the impact of the COVID-19 pandemic on the primary efficacy analysis (see also section 7.4.7 below). No intercurrent events with relevant impact on interpretation of analysis results were identified. Thus, no additional sensitivity analyses were considered necessary.

[figure not shown]

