In addition to the blinded safety data evaluation (once all subjects of stage 1 completed Day 30±7 Follow-up Observational Visit V4), an interim analysis will be performed once complete 180-day data (V9) of stage 1 are available. Data will be unblinded for sponsor staff and vendor data management and biostatistics staff only with regard to stage 1 subject's assignment to treatment groups. The blind for subjects in stage 2 will be maintained. Stage 2 subjects will not be included in the 180-day interim analysis.

An interim analysis of complete stage 1 MP data will be performed as soon as data until and including the End of MP visit V15 from stage 1 subjects are completely available (except for missingness due to premature study discontinuation or intermittently missing visits). The analysis of stage 1 MP data will serve to get further insights regarding duration of effect and occurrence of TEAEs over the entire Main Period of up to 360 days. Knowledge gained from the interim analysis at End of MP of stage 1 will be useful to decide whether it is still meaningful to motivate stage 2 subjects affected by COVID-19 (see section 7.4.7) to re-assume on-site visits depending on the number of missing visits for the primary efficacy variable. Since ensuring the safety of subjects is paramount, this analysis will be valuable to balance the potential risks of further on-site visits against benefits such as avoidance of missing data and premature study discontinuations. Investigators and subjects, site staff and blinded monitor will be kept blinded throughout for both stages until final unblinding. The blind for subjects in stage 2 will be completely maintained.

Stage 2 of the study

No safety concerns were raised during DEM. Therefore, stage 2 of the study was started. After successful screening, eligible subjects are enrolled and randomized at the Baseline Visit V2 (Day 1) to one of two dose groups of 20 U (n=30) or 100 U NT 201 (n = 60) according to randomization ratio 1:2.

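### The only randomised comparison for 100 U, against 20 U in stage 2, is not specified with a confidence interval in the visible plan

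*SAP*

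**What the plan says.** SAP 3.1 states that stage 2 subjects are "randomized at the Baseline Visit V2 (Day 1) to one of two dose groups of 20 U (n=30) or 100 U NT 201", in a 1:2 ratio with 60 planned on 100 U. Stage 1 has 30 subjects on 20 U and 60 each on 50 U and 75 U, with none on 100 U.

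For the primary variable, SAP 7.1.1 plans pairwise log-rank tests of each high dose against 20 U and adds: "The 20 U group data will be pooled from stage 1 and 2 for the final analysis." The Cox model has dose group, study site and baseline FWS score as covariates. Stage is not among them, and Protocol 12.4.1.1 agrees. The stated output is: "Hazard ratios will be calculated for each dose group to the reference group including Wald 95% confidence intervals and two-sided p-values."

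A sensitivity model to explore stage effects uses "dose groups 20 (stage 1), 20 (stage 2), 50, 75 and 100 U with 20 (stage 1) as reference group". The follow-up is left open: "Depending on the outcome further exploration might be needed." Under SAP 7.1.2 the secondary duration variables are handled in the same way, "except for the sensitivity analysis with separate 20 U groups from stage 1 and 2, which will be only done for the primary variable".

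A second sensitivity analysis deals with COVID-19 by having "time to relapse to baseline status from affected cases being censored at the first visit of those subsequent visits with missing values", where the gap runs up to the observed relapse. After the final BDRM on 7-JAN-2021, the SAP records that "the above-specified analysis to account for a specific pattern of missingness due to COVID-19 pandemic was deemed adequate and sufficient". SAP 7.4.7 points to the stage split of 20 U already in 7.1.1, and no further sensitivity analysis was added.

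**The concern.** Stage 2 exists to study 100 U, and Protocol 6.2 gives blinding and comparability as the reasons for repeating 20 U there. In the pooled analysis, 30 of the 60 planned comparators for 100 U are non-concurrent. In the five-group model the reference is 20 U (stage 1). That gives 50 U and 75 U their randomised contrast, but it makes the 100 U hazard ratio entirely cross-stage.

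The documents themselves give a reason to expect a difference between stages. Protocol 12.4.7.6 and SAP 7.4.7 say that missed on-site visits in stage 2 can make time to relapse look too long, and that stage 1 is unaffected. Against stage 1 or pooled controls, such a lengthening can look like a benefit of 100 U. The contrast with 20 U (stage 2) removes whatever is common to stage 2. Protocol 12.4.7.6 expected that separate stage analyses would probably be needed.

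The COVID-19 censoring analysis is not a substitute. It censors only subjects whose relapse was seen after missed visits, so it removes stage 2 events and can push the cross-stage hazard ratio further down.

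**Working it through.** **Allocation.** 150 subjects at 1:2:2 give 30/60/60, and 90 at 1:2 give 30/60. The total of 240 agrees with the Protocol synopsis. The visible sample-size text gives no power, effect size or event rate to reproduce.

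**What each planned hazard ratio estimates.** Let s be the log hazard ratio of stage 2 versus stage 1, with no dose effect.

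- Against 20 U (stage 1), the 100 U log hazard ratio is s.
- Against pooled 20 U, half of whom are in stage 2, it is about 0.5·s.
- Against 20 U (stage 2), it is 0.

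For assumed stage hazard ratios of 0.9, 0.8 and 0.7, the pooled value is √0.9 = 0.95, √0.8 = 0.89 and √0.7 = 0.84.

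**Simulation with an assumed stage effect.** Groups of 30/30/60/60/60, Weibull shape 2, 20 U median 180 days, visits every 30 days to Day 360, Efron ties, 2000 trials each, no dose effect:

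| Stage HR | vs 20 U stage 1 (CI coverage) | vs pooled 20 U (coverage) | vs 20 U stage 2 (coverage) | Stage check p<0.05 |
|---|---|---|---|---|
| 0.9 | 0.90 (92%) | 0.96 (95%) | 1.00 (95%) | 7% |
| 0.8 | 0.79 (82%) | 0.90 (92%) | 1.00 (96%) | 15% |
| 0.7 | 0.70 (67%) | 0.85 (87%) | 1.00 (95%) | 26% |

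A separate run with exponential times (600 trials) at stage HR 0.8 gave 0.80, 0.90 and 1.01. Adding 9 sites and baseline FWS to the model (400 trials, assumed site SD 0.3 and baseline log HR 0.3) gave 0.78, 0.89 and 0.99. The 30 versus 30 stage check would seldom reach p<0.05 at stage effects of this size, so it is a weak trigger for further exploration.

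**Simulation with missed visits.** No dose effect; 20 U medians of 150, 180 and 210 days; with or without an unplanned return visit; 18 cells of 400–600 trials (Monte Carlo error about 0.01). The gap starts uniformly between Day 154 and Day 229. These are the stage 2 positions on 11-MAR-2020 for a subject randomised on 10-OCT-2019 and for one randomised three days after the DEM of 24-JUL-2019.

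| Assumed pattern in stage 2 | vs stage 1 | vs pooled | vs pooled, COVID-19 censoring rule |
|---|---|---|---|
| 25% miss 60 days | 0.96–1.00 | 0.98–1.00 | 0.96–0.98 |
| 50% miss 90 days | 0.87–0.94 | 0.93–0.97 | 0.89–0.93 |
| 75% miss 120 days | 0.75–0.87 | 0.88–0.94 | 0.82–0.90 |

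The contrast with 20 U (stage 2) stays at 0.99–1.01 without censoring and 0.99–1.02 with it. The censoring rule lowered the pooled value in 17 of 18 cells.

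**Precision, if all subjects relapse.**

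- SE of the contrast with stage 2: √(1/60 + 1/30) = 0.224.
- SE of the pooled comparison: √(1/60 + 1/60) = 0.183, a ratio of 1.22.
- Power at a true HR of 0.6 (two-sided 5% assumed): 63% against 80%.
- RMSE break-even: pooled bias √(0.224² − 0.183²) = 0.129, hence s = −0.258 and a stage HR of 0.77. The simulation puts it between 0.70 and 0.77.

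**Can a reader rebuild the contrast?** The point estimate is the ratio of two planned hazard ratios. The CI needs their covariance. Approximating the SE by √(SE₁² + SE₂² − 2/reference events) gave 0.256 against a true 0.244 with covariates in the model (median error 4.6%, largest 15%).

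**The case against.** The pooled analysis is deliberate, disclosed and usually the better single estimate. Its RMSE was lower in all 24 missed-visit cells without censoring (the 18 above plus 6 at a true HR of 0.6). It was also lower at an assumed stage HR of 0.8 (0.216 versus 0.232), though not at 0.7 (0.255 versus 0.245). At a true HR of 0.6, the worst uncensored pooled value was 0.56, a log bias of about 0.07 against an SE of 0.183. All of this stands and is a reason to keep the pooled result.

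Because each high dose sits in a single stage, the five-group model is equivalent to dose plus stage. Stage is therefore modelled in a prespecified sensitivity analysis whose stated aim is to explore stage effects, and it serves that aim. This also stands: the gap is one unlisted contrast in a model that will be fitted anyway.

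The final BDRM reviewed the actual missing data and found random missingness reasonable, whereas the stage effects used here are assumed. SAP 7.4.7 also rules out a pandemic effect on baseline characteristics. That does not cover missed visits after baseline or other differences between stages, and only the contrast would show whether the bias was in fact small.

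Text is redacted just before the log-rank sentence in both documents, and after the sentence on further exploration in Protocol 12.4.1.1. SAP 7.1.2 can also be read as already planning Kaplan-Meier curves with 20 U split by stage. Part of the fix may therefore exist already, and the sponsor would only need to confirm it.

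**Conclusion.** The point holds on the visible text and should be fixed. 100 U is compared with pooled 20 U without a stage term, its hazard ratio in the sensitivity model is fully cross-stage, and the randomised contrast with 20 U (stage 2) is not specified with a CI.

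The size depends on stage effects and missed-visit rates that the documents do not give. Over the assumed range, a null 100 U effect appears as a pooled hazard ratio between 0.85 and 1.00, and as low as 0.82 under the COVID-19 censoring rule. With few missed visits the bias is small. The tests are exploratory and no multiplicity adjustment is foreseen, so this concerns how the 100 U estimate is read and is not a claim about error rates. Confidence is medium because of the redactions and the assumed inputs.

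**What to change.** Keep the pooled analysis and the planned reference group, and add for the primary variable:

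- the contrast 100 U versus 20 U (stage 2) from the same five-group Cox model, with Wald 95% CI and two-sided p-value;
- a log-rank test within stage 2;
- Kaplan-Meier curves with 20 U split by stage.

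Report these beside the pooled estimate as exploratory sensitivity results, whatever the stage check shows. Optionally, output the same contrast once under the COVID-19 censoring analysis.

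State the limit: bias that depends on dose can remain, because 20 U and 100 U subjects may relapse at different times relative to the disruption. At a true HR of 0.6 in the missed-visit cells, the contrast gave 0.60–0.63 (pooled 0.56–0.60). Under the censoring rule it gave 0.55–0.60 (pooled 0.46–0.58).

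The programming cost is one contrast statement, one test and one figure, with no new data. The statistical cost is the wider interval and lower power of the added estimate, so it should not replace the pooled one.
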